**Fig. 3. Renin-angiotensin system.**

#### ACE2

ACE2 is a monocarboxypeptidase primarily expressed in vascular endothelial cells and renal tubular epithelium. The catalytic domain of ACE2 shares 42% identity with that of angio-

converting enzyme (ACE); however, unlike ACE, ACE2 activity is not inhibited by ACE inhibitors. The membrane-bound ectodomain of ACE2 can be cleaved by the metalloproteinase ADAM17, releasing a soluble form of ACE2. Thus, measuring plasma ACE2 reflects the level of soluble ACE2. Soluble ACE2 levels and activity in plasma are elevated in patients with chronic heart failure, cardiac dysfunction, and myocardial infarction. While ACE2 is believed to play a key role in cardiac protection, the exact mechanisms remain unclear.

### ***Angiotensin (1-7)***

Angiotensin (1-7) is primarily produced from angiotensin II by ACE2, with the heart, brain, and kidneys serving as key sites of its generation. It exerts broad effects on the cardiovascular system, including vasodilation, myocardial protection, antiarrhythmic actions, and antihypertensive effects. Additionally, it may inhibit vascular inflammation and smooth muscle cell proliferation via the Mas receptor. Angiotensin (1-7) is also believed to have beneficial effects on metabolism by reducing insulin resistance

### ***Pro-B-type natriuretic peptide***

Cardiac natriuretic peptides are released by the heart under physiological conditions and play a key role in maintaining cardiovascular homeostasis. They induce dilation of afferent arterioles and constriction of efferent arterioles in the kidneys, which increases glomerular filtration, promoting natriuresis and diuresis. Additionally, these peptides reduce cardiac preload by shifting intravascular fluid into the interstitial space. Natriuretic peptides also suppress the RAS, inhibiting renin release from the kidneys and aldosterone secretion from the adrenal glands, further enhancing natriuresis and reducing extracellular fluid volume. B-type natriuretic peptide (BNP) belongs to the natriuretic peptide family, which includes atrial natriuretic peptide (ANP) and C-type natriuretic peptide, the latter primarily secreted by the vascular endothelium. ANP and BNP are secreted by cardiac myocytes, with BNP predominantly released by atrial myocytes in a healthy heart. However, in congestive HF, ventricular BNP secretion increases significantly, reflecting greater ventricular stress and severe cardiac dysfunction. In patients with HF, BNP levels can rise by up to 107-fold compared to healthy individuals.

### ***High-sensitivity C-reactive protein***

Increased levels of the inflammatory biomarker high-sensitivity C-reactive protein (hsCRP) are predictive of cardiovascular events. In a trial involving apparently healthy individuals without hyperlipidemia but with elevated hsCRP, the lipid-lowering drug rosuvastatin significantly reduced hsCRP levels by 37% and lowered the incidence of major cardiovascular events [12]. hsCRP concentrations were measured using enzyme-linked immunosorbent assay kits from BD Biosciences Pharmingen (BD Biosciences Pharmingen, Heidelberg, Germany).

## **6. Study outcomes**

### **6.1. Primary outcome**

- Changes in LVGLS after ertugliflozin treatment in individuals with T2D and pre-HF compared to placebo.

### **6.2. Secondary outcomes**

- Changes in LVEF
- Changes in LVMI
- Changes in E/e'
- Changes in left atrial volume index
- Changes in LV end-diastolic volume

### **6.3. Prespecified exploratory outcomes**

- Changes in body weight, body fat mass, and body fat percentage with ertugliflozin
- Whether ertugliflozin reduces microalbuminuria
- Impact of ertugliflozin on ACE2, angiotensin (1-7), pro-BNP, and hsCRP levels
- Cardiovascular benefits of ertugliflozin, including improvement in diastolic dysfunction and activation of the ACE2-angiotensin (1-7) axis

### **6.4. Safety outcome**

- Adverse events related to ertugliflozin treatment in individuals with T2D and pre-HF

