## **3. Study design**

[figure not shown]
This randomized, double-blind, placebo-controlled, parallel-group trial aims to enroll 120 participants. Individuals with T2D who have been on pharmacological treatment for at least 12 weeks, without any dose adjustments prior to enrollment, will be eligible for screening. The screening period will last up to two weeks before randomization. To qualify for randomization, participants must meet an 80% compliance rate, based on pill count, and the investigator's discretion during the run-in phase. After randomization, participants will be blinded to their glycated hemoglobin (HbA1c) and fasting plasma glucose (FPG) results. To maintain blinding, urinary glucose excretion (UGE) results will also be masked from participants. Urine glucose, albumin, calcium, and creatinine will be measured separately during on-site visits.

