## 7. Treatment

### 7.1. Intervention and control

After randomization, patients will undergo a 24-week double-blind treatment period. A total of 102 patients aged 20 years or older will be randomly assigned in a 1:1 ratio to one of the following two groups:

- Ertugliflozin 5 mg once daily
- Placebo (identical in appearance to ertugliflozin) once daily

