### 7.2. Rescue therapy

The following criteria will trigger alerts: 1) FPG >270 mg/dL (13.3 mmol/L) at the Week 8 visit; 2) FPG >240 mg/dL (11.1 mmol/L) at the Week 16 visit.

Open-label rescue medication(s) to manage hyperglycemia will be administered at the investigator's discretion, following local standards of care and prescribing practices. Any approved medication, including oral antidiabetic drugs or insulin, may be used to treat hyperglycemia, with the exception of other SGLT2 inhibitors. If glycemic rescue is necessary, the investigational product administered during the randomized, double-blind treatment phase should be continued, and blinding must be maintained until the end of the study.

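### The only safety outcome is worded as adverse events related to ertugliflozin, with no causality method and no all-cause or serious adverse event summary by arm

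*Combined protocol and SAP*

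**What the plan says.** Section 6.4 (Safety outcome) has one entry: "Adverse events related to ertugliflozin treatment in individuals with T2D and pre-HF". The document supplied says nothing else about adverse events. It gives no definition or collection window, no causality scale or assessor, no serious or all-cause adverse event outcome, no safety analysis set and no safety summary by arm.

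The design is described in Section 3 as "This randomized, double-blind, placebo-controlled, parallel-group trial". Section 7.1 specifies the control as "Placebo (identical in appearance to ertugliflozin) once daily", and Section 7.2 adds, for patients given glycaemic rescue, that "blinding must be maintained until the end of the study". The primary outcome in Section 6.1 names its comparator: "Changes in LVGLS after ertugliflozin treatment in individuals with T2D and pre-HF compared to placebo". The safety line names none.

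**The concern.** In a randomised placebo-controlled trial, the rates of all adverse events in the two arms can be compared without anyone deciding what caused each event. An outcome restricted to related events gives that up, because an event enters only after someone has attributed it. The plan does not say who does this, on what scale, or whether the assessor knows anything that hints at the arm.

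Two things are at stake. First, events not attributed to the drug drop out, and unexpected harms are among the likeliest to go unattributed. In a trial with 51 or 60 patients per arm, few cases of any one event will occur, so losing some of them matters. Second, if events are attributed more readily in one arm than in the other, the reported rates can differ when the true rates do not, or agree when the true rates differ.

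**Working it through.** The plan has no safety figure to reproduce: no event rate, margin or test. The check is therefore a reading of the text, followed by illustrations with assumed rates.

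**Step 1: the text.** Section 6.1 states a contrast with placebo; Section 6.4 states a class of events defined by relation to ertugliflozin. No other section supplies an all-cause or serious adverse event outcome that would make up for the restriction.

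**Step 2: inputs.**
- Patients per arm, from the document: 51 (Section 7.1: "A total of 102 patients aged 20 years or older will be randomly assigned in a 1:1 ratio") or 60 (half of the 120 in Section 3). The document gives both totals, so both are used.
- Event risks and attribution shares: all assumed; none is in the document.

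**Step 3: chance that a harm appears at all in the treated arm.** Let the true risk be 5% and let a share k of events be attributed. Then P(at least one recorded) = 1 − (1 − 0.05k)^n.

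| k | n = 51 | n = 60 |
|---|---|---|
| 1 (all events count) | 1 − 0.95^51 = 0.927 | 1 − 0.95^60 = 0.954 |
| 0.5 | 1 − 0.975^51 = 0.725 | 1 − 0.975^60 = 0.781 |
| 0.25 | 1 − 0.9875^51 = 0.474 | 1 − 0.9875^60 = 0.530 |

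This concerns detection in one arm. It says nothing yet about the contrast between arms.

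**Step 4: contrast between arms, equal attribution.** Assume true risks of 35% on drug and 20% on placebo, with a share q attributed in both arms. The recorded difference is q × 15 percentage points. Power (normal approximation, two-sided 5%, n = 51 per arm) is Φ[(d − 1.96·SE0)/SE1], where d = p1 − p2, SE0 = √(2·p̄(1 − p̄)/n), p̄ is the mean of the two risks, and SE1 = √((p1(1 − p1) + p2(1 − p2))/n).

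- q = 1: d = 0.15, SE0 = 0.0884, SE1 = 0.0872, power about 39%.
- q = 0.5: d = 0.075, SE0 = 0.0682, SE1 = 0.0678, power about 19%.
- By the same formula, q = 0.75 gives d = 0.1125 and about 29%; q = 0.25 gives d = 0.0375 and about 11%.

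With assumed risks of 45% and 30%, power falls from about 34% (q = 1) to about 24%, 16% and 9% for q = 0.75, 0.5 and 0.25. The trial is not sized for safety, so these figures show only the direction and rough scale of the loss.

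**Step 5: contrast between arms, unequal attribution.** Assume 20% of patients in each arm have an event, with 50% attributed on drug and 25% on placebo. The recorded rates are 0.20 × 0.50 = 10% and 0.20 × 0.25 = 5%: a difference where none exists. If the shares are equal, a true null stays null.

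**Step 6: could attribution differ here?** Section 3 withholds HbA1c, fasting glucose and urinary glucose results from participants ("To maintain blinding, urinary glucose excretion (UGE) results will also be masked from participants"). It does not say that those results are withheld from investigators, and Section 7.2 sets fasting glucose alerts and leaves rescue to the investigator. The person judging relatedness might therefore hold clues to the arm. The document neither shows nor excludes this.

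**The case against.** A reader might infer that the outcome has no meaning in the placebo arm, since a patient who never took ertugliflozin cannot have an event related to it. The document does not support that. With a double-blind design and an identical placebo, a blinded assessor would judge relatedness to study drug in both arms. Placebo events can be classed as related, and the comparison can still be interpreted.

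A reader might also infer that the plan specifies a between-arm safety comparison filtered by causality. It specifies no safety table, test or causality step, so the filter follows from the wording and is not a stated procedure.

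The best defence is that the wording is merely loose. Sections 6.1 and 6.3 also describe outcomes in terms of ertugliflozin's effect, and nobody would take the body-weight outcome to be measured in one arm only. On that reading, Section 6.4 simply means adverse events during treatment. This reading is possible, and if it is the intended one, rewording only records the intent. It does not remove the point: the line as it stands can be followed literally, and nothing else in the document prevents that.

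It is also fair to say that relatedness does not require a harm to be already known, that every rate in the illustrations is assumed, and that the 10% versus 5% example needs attribution to differ by arm.

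**Conclusion.** The concern holds in a limited form. The sole safety outcome, as written, depends on a causality judgement with no stated method and omits unattributed events, and no all-cause or serious adverse event summary by arm is stated.

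The loss of signal needs only that some events go unattributed. With the assumed 5% risk, the chance of seeing at least one case among 51 treated patients falls by about 20 percentage points (93% to 73%) if half are attributed. Bias between arms is conditional on unequal attribution, which remains a possibility and is not a finding.

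The primary outcome and the sample size are untouched. The change should be made because it is cheap and settles which events count before unblinding.

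**What to change.** Reword Section 6.4 along these lines: all adverse events and all serious adverse events from first dose to end of follow-up, regardless of attributed causality, with the number and percentage of patients in each arm. Report relatedness to blinded study drug as a descriptive subset, and state who assesses it and on what scale. A risk difference with 95% confidence interval is optional.

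The cost is one reworded line and a slightly longer safety table. The document does not describe how adverse events are collected. If all events are already recorded, nothing else changes; if only attributed events are recorded, the collection form would need to be widened to match.

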## 7. Treatment

### 7.1. Intervention and control

After randomization, patients will undergo a 24-week double-blind treatment period. A total of 102 patients aged 20 years or older will be randomly assigned in a 1:1 ratio to one of the following two groups:

- Ertugliflozin 5 mg once daily
- Placebo (identical in appearance to ertugliflozin) once daily

### 7.2. Rescue therapy

The following criteria will trigger alerts: 1) FPG >270 mg/dL (13.3 mmol/L) at the Week 8 visit; 2) FPG >240 mg/dL (11.1 mmol/L) at the Week 16 visit.

Open-label rescue medication(s) to manage hyperglycemia will be administered at the investigator's discretion, following local standards of care and prescribing practices. Any approved medication, including oral antidiabetic drugs or insulin, may be used to treat hyperglycemia, with the exception of other SGLT2 inhibitors. If glycemic rescue is necessary, the investigational product administered during the randomized, double-blind treatment phase should be continued, and blinding must be maintained until the end of the study.

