**Fig. 1. Stages in the development of HF and recommended therapy by stage [1].**

## 4.2. Exclusion criteria

- Individuals with type 1 diabetes
- Age  $<20$  years at the time of screening
- HbA1c  $<7.0\%$  or  $>9.5\%$  at screening
- FPG  $>15$  mmol/L (270 mg/dL) at screening (Visit 1), confirmed by a repeat test prior to randomization
- Use of a glucagon-like peptide-1 (GLP-1) receptor agonist within 12 weeks prior to the screening visit

- Women of childbearing potential without an effective contraceptive method
- History of gastric surgery, including gastric banding, within 3 years before the screening visit
- History of diabetic ketoacidosis or nonketotic hyperosmolar coma prior to screening.
- Mean systolic blood pressure (BP)  $>180$  mmHg or diastolic BP  $>95$  mmHg after three separate measurements
- History or current symptoms of HF
- Severe anemia, or severe respiratory, hepatic, neurological, or psychiatric disorders; active malignant neoplasms; or any major systemic disease or short life expectancy that would hinder protocol implementation or interpretation of study results
- Aspartate aminotransferase (AST) or alanine aminotransferase (ALT) levels more than three times the upper limit of normal (ULN)
- Total bilirubin  $>1.5$  times the ULN (except for Gilbert syndrome)
- Use of systemic glucocorticoids (excluding topical, ophthalmic, or inhaled forms) for more than 10 consecutive days within 90 days prior to screening
- Participation in another investigational drug trial or use of prohibited therapies within 3 months prior to screening

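### The two rescue-alert glucose thresholds in Section 7.2 are each given in mg/dL and mmol/L values that do not match, by about 31 mg/dL at Week 8 and 40 mg/dL at Week 16

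*Combined protocol and SAP*

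**What the plan says.** Section 7.2 (Rescue therapy) defines two on-treatment alerts for fasting plasma glucose (FPG), each in two units: "FPG >270 mg/dL (13.3 mmol/L) at the Week 8 visit; 2) FPG >240 mg/dL (11.1 mmol/L) at the Week 16 visit". What follows an alert is not mandated. Open-label rescue is given at the investigator's "discretion, following local standards of care and prescribing practices", and if rescue is needed, "the investigational product administered during the randomized, double-blind treatment phase should be continued".

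Two other places bear on the point:

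- Section 4.2 (Exclusion criteria) excludes anyone with FPG above 15 "mmol/L (270 mg/dL) at screening (Visit 1), confirmed by a repeat test prior to randomization". It therefore carries its own mg/dL to mmol/L equivalence for the same measurement.
- Section 3 (Study design) masks glucose results from participants: "After randomization, participants will be blinded to their glycated hemoglobin (HbA1c) and fasting plasma glucose (FPG) results".

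No section names a governing unit. Section 4.2 writes mmol/L first and Section 7.2 writes mg/dL first.

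**The concern.** The protocol gives 270 mg/dL two different mmol/L values: 15 at screening and 13.3 at Week 8. The Week 16 pair has no direct counterpart elsewhere, but it fails under the same conversion factor. As written, each alert can be read as either of two thresholds.

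These are the only numeric glycaemic alerts in the document for the 24-week treatment period. Between the two readings lies a band of FPG values that alerts under one unit and not under the other. Both bands lie below the 270 mg/dL entry ceiling in Section 4.2, so the FPG criterion on its own does not keep people with such values out. Participants do not see their FPG, so the response to a high value rests with the site.

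There is also a possible link to the primary endpoint. Rescue is a glucose-lowering co-intervention, and Section 8 itself cites a study in which better glycaemic control over 12 months went with a 21% improvement in GLS. The documents do not allow the size of any such effect in this trial to be worked out.

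**Working it through.** **Inputs**

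- Week 8 alert: 270 mg/dL, stated as 13.3 mmol/L (Section 7.2).
- Week 16 alert: 240 mg/dL, stated as 11.1 mmol/L (Section 7.2).
- Screening limit: 15 mmol/L, stated as 270 mg/dL (Section 4.2).

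**Step 1. The conversion factor, from the protocol itself.** Section 4.2 gives 270 / 15 = 18.0 mg/dL per mmol/L.

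**Step 2. The factors implied by Section 7.2.**

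- Week 8: 270 / 13.3 = 20.30
- Week 16: 240 / 11.1 = 21.62

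The stated figures cannot be reproduced. The two implied factors differ from 18 and from each other.

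**Step 3. Convert in both directions at 18.**

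| Visit | Stated mg/dL | Correct mmol/L | Stated mmol/L | Correct mg/dL | Gap, mg/dL | Gap, mmol/L |
|---|---|---|---|---|---|---|
| Week 8 | 270 | 270 / 18 = 15.0 | 13.3 | 13.3 × 18 = 239.4 | 270 − 239.4 = 30.6 | 15.0 − 13.3 = 1.7 |
| Week 16 | 240 | 240 / 18 = 13.33 | 11.1 | 11.1 × 18 = 199.8 | 240 − 199.8 = 40.2 | 13.33 − 11.1 = 2.23 |

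**Step 4. Sensitivity to the factor.** A slightly more precise factor of 18.016 (molar mass of glucose about 180.16 g/mol, an assumption from basic chemistry) gives 14.99 and 13.32 mmol/L, and in reverse 239.6 and 200.0 mg/dL. The choice of factor does not explain the mismatch.

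**Step 5. Who falls between the two readings.**

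- Week 8, about 240 to 270 mg/dL. Example: 250 / 18 = 13.9 mmol/L, which is above 13.3, while 250 is below 270.
- Week 16, about 200 to 240 mg/dL. Example: 220 / 18 = 12.2 mmol/L, which is above 11.1, while 220 is below 240.

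Both examples alert in mmol/L and not in mg/dL.

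**A likely source.** The values 270, 240 and 200 mg/dL convert to 15.0, 13.3 and 11.1 mmol/L. The mmol/L figure printed for Week 8 is the right conversion of the mg/dL figure printed for Week 16, as if the mmol/L values had slipped one step. That is an inference. It does not show which column was meant.

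**The case against.** The strongest reply is that Section 7.2 writes mg/dL first and puts mmol/L in brackets. An ordinary reader takes the leading figure as the criterion and the bracket as a conversion, so the thresholds are defined and only the conversions are wrong. This is a reasonable presumption, but the text does not state it, and Section 4.2 uses the opposite order. An intended 13.3 and 11.1 mmol/L cannot be ruled out.

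A second reply concerns safety. Section 3 masks FPG from participants and does not say that investigators are masked. Section 7.2 leaves rescue to the investigator and nowhere bars it below the threshold, so a site that sees 250 mg/dL at Week 8 can treat whichever unit drives the alert. This stands, and it is why the safety consequence is modest. What remains is that the alert, whose purpose is to prompt that decision, has two possible values.

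Third, FPG is not the only glycaemic limit on entry. Section 4.2 also excludes HbA1c above 9.5% at screening, and the documents do not show how many participants would fall in the affected bands. This also stands.

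Fourth, rescue is not a listed outcome in Section 6, and study drug continues after it. No effect on the LVGLS comparison has been shown, and none is claimed here.

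**Conclusion.** The concern holds. Both unit pairs in Section 7.2 are wrong as written: the mmol/L equivalents of 270 and 240 mg/dL are 15.0 and 13.3, not 13.3 and 11.1. The mismatch is 30.6 mg/dL at Week 8 and 40.2 mg/dL at Week 16. The result rests only on the factor of 18 that Section 4.2 supplies.

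The practical weight is limited. If every site uses one unit, participants are handled alike and the defect is that the intended threshold is unknown. Only if sites use different units are participants with the same FPG handled differently. The share of participants affected, and any effect on LVGLS, cannot be computed from the documents. Sample size and type I error are unaffected. It should be fixed because staff act on this threshold and the correction costs almost nothing.

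**What to change.** The sponsor should state which values are intended and correct the paired unit at 18 mg/dL per mmol/L:

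- If the mg/dL values are intended: above 270 mg/dL (15.0 mmol/L) at Week 8 and above 240 mg/dL (13.3 mmol/L) at Week 16.
- If the mmol/L values are intended: above 13.3 mmol/L (240 mg/dL) at Week 8 and above 11.1 mmol/L (200 mg/dL) at Week 16.

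The protocol should also name one governing unit for the alert. This review takes no position on which threshold is clinically right.

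The cost is a one-line protocol correction and a check of the value and unit actually used to raise alerts, whether at the laboratory or at the site; the protocol does not say which.

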## 8. Sample size calculation

The primary endpoint of this study is the change in LVGLS from baseline to week 24. The hypothesis is that the ertugliflozin group will demonstrate superiority over the placebo group.

- Null hypothesis ( $H_0$ ):  $P_1 = P_2 \geq \delta$
- Alternative hypothesis ( $H_1$ ):  $P_1 - P_2 < \delta$

The following equation will be used for sample size estimation:

When  $r = 1$ ,

1. Type I error ( $\alpha$ ) = 5% (two-sided, default)
2. Power = 1 – Type II error ( $\beta$ ) = 80% (default)
3. Allocation ( $r$ ) = 1 (default)
4. Mean in the ertugliflozin group ( $\mu_1$ )
5. Mean in the placebo group ( $\mu_2$ )

6. Standard deviation (SD) in the ertugliflozin group ( $SD_1$ )
7. SD in the placebo group ( $SD_2$ )
8. Dropout rate ( $d$ ) = 10% (default)

Since no prior interventional studies have evaluated the effect of ertugliflozin on GLS, we referenced studies measuring LV volume. An increase in LV volume has been used as a marker for assessing the impact of drug therapy on heart failure survival [13]. It has been suggested that a 10 mL change in LV volume is clinically significant [14]. This change corresponds to a 15% change in EF in individuals with pre-HF, whose EF typically ranges from 30% to 50%. In heart failure populations, the SD for the mean difference in LV volume has been reported to be 7.5 [15]. For comparison, the EMPA-REG OUTCOME trial showed that empagliflozin reduced heart failure hospitalization by 35% [16], and the CANVAS program found that canagliflozin reduced heart failure hospitalization by 33% [17]. Based on these results, we assumed a 15% baseline GLS in both groups and a 13.2% decrease in GLS in the ertugliflozin group after treatment, with no change in the placebo group. We assumed a standard deviation of 3.5 for both groups, adopting a conservative approach. Considering an 18% dropout rate, the minimum required sample size is 100 participants (60 per group with a 1:1 randomization). Additionally, a recent study demonstrated that improvements in glycemic control (HbA1c reduction from  $10.3 \pm 2.4\%$  to  $8.3 \pm 2.0\%$ ) over a 12-month period led to a 21% improvement in GLS and a 24% improvement in cardiac function, as estimated by septal e' [18].

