## **2. Hypothesis**

We hypothesize that ertugliflozin will improve cardiac function in individuals with T2D and pre-heart failure.

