## **4. Study participants**

### **4.1. Inclusion criteria**

- Individuals with T2D on stable oral antidiabetic medications, excluding SGLT2 inhibitors, for at least 12 weeks prior to enrollment, with no dose adjustments
- Estimated glomerular filtration rate (eGFR)  $\geq 45$  mL/min/1.73 m^2
- Pre-heart failure (pre-HF), or stage B heart failure (HF), identified based on structural or functional markers (Fig. 1) [1, 2]:
  - Structural abnormality defined as moderate left ventricular hypertrophy (LVH),

- indicated by a left ventricular mass index (LVMI)  $\geq 95$  g/m^2 in women or  $\geq 115$  g/m^2 in men
- Functional impairment defined as E/e'  $> 15$  and/or left ventricular global longitudinal strain (LVGLS)  $> -16\%$

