## 5. Major investigation

### 5.1. GLS by transcardiac echocardiography

The standard commercially available cardiac ultrasound machines (Vivid 7 and Vivid E9, General Electric Medical Systems, Milwaukee, WI, USA) will be used to perform resting echocardiograms. Images will be saved in raw data format for offline analysis to assess left ventricular (LV) wall thickness, valvular morphology, chamber volumes, and global 2D strain. LV mass will be measured using standard criteria and normalized to body surface area to obtain the LVMI [3]. LVH will be determined following the recommendations of the American Society of Echocardiography and the European Association of Echocardiography [4]. The modified Simpson's biplane method will be used to measure the LV ejection fraction (LVEF).

[figure not shown]
Pulsed wave Doppler recordings of LV inflow will be acquired from the apical four-chamber view with the sample volume placed between the tips of the mitral leaflets. Peak early (E) and late diastolic flow velocities (A), the E/A ratio, and deceleration time of early diastolic flow will be measured. Pulsed wave tissue Doppler will be performed to assess peak early

diastolic mitral annular velocity ( $e'$ ). The ratio of mitral inflow early diastolic velocity to the average  $e'$  velocity obtained from the septal and lateral sides of the mitral annulus ( $E/e'$ ) will be calculated to estimate LV filling pressure, with a value  $>15$  indicating elevated LV filling pressure [5].

For global 2D strain analysis, digital loops will be acquired from standard apical four-chamber, three-chamber, and two-chamber views. The LV endocardial border will be traced at the end-systolic frame. The strain curve will be derived from the gray-scale images using dedicated software (EchoPAC, GE, Vingmed, Norway). Peak strain will be defined as the peak negative value on the strain curve during the cardiac cycle. Peak GLS will be calculated for the entire U-shaped LV myocardium as:  $LVGLS (\%) = [(L \text{ end-systole} - L \text{ end-diastole}) / L \text{ end-diastole}] \times 100$  [6], where “ $L$ ” represents the length of the entire LV myocardium, considered as one continuous segment. GLS will be averaged across the apical 4-, 3-, and 2-chamber views.

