A recent study demonstrated a strong positive correlation between GLS and ejection fraction (EF), particularly in individuals with LV systolic impairment ( $r=0.95$ ;  $P<0.001$ ) [7]. In contrast, LV ejection had a relatively weaker correlation with LV twist and torsion. Another study also showed that semi-automated GLS analysis had a strong correlation with EF, regardless of whether it was performed by experienced readers ( $r=0.98$ ) or less experienced readers ( $r=0.91$ ) (Fig. 2) [8]. The semi-automated GLS measurements exhibited less bias between experienced and less experienced readers ( $-1.0 \pm 13\%$ ) compared to EF measurements ( $-3.5 \pm 6.7\%$ ). Furthermore, repeated GLS measurements showed higher intra-class correlation ( $ICC=0.98$ ) compared to EF ( $ICC=0.89$ ). GLS analysis also takes less time, approximately one minute per patient, whereas biplane EF measurements take twice as long. Thus, semi-automated GLS measurements are faster, less dependent on experience, and more reproducible than conventional EF measurements.

In a recent study involving individuals with advanced chronic kidney disease, GLS was found to be a significant predictor of all-cause mortality [hazard ratio (HR), 1.09; 95% confidence interval (CI), 1.02–1.16;  $P<0.05$ ] and cardiovascular (CV) mortality (HR, 1.16; 95% CI, 1.04–1.30;  $P<0.05$ ), even after adjusting for clinical factors such as LVMI and EF [9]. Notably, GLS had greater predictive power for both all-cause and CV mortality compared to EF. Impaired GLS ( $>-16\%$ ) was associated with a 5.6-fold increased risk of CV mortality, even in individuals with preserved EF. Collectively, these findings suggest that GLS is a valuable measure for reflecting myocardial function.

**Fig. 2. Left ventricular global longitudinal strain and volumes.** After the endocardial boundaries are defined by the user, the software generates global longitudinal strain curves throughout the cardiac cycle. These curves quantify myocardial deformation, represented as strain values, across the 4-chamber, 3-chamber, and 2-chamber views [8].

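### Do the undefined symbols and the missing minus sign in Section 8's hypotheses leave the primary test unclear?

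*Combined protocol and SAP*

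**What the plan says.** Section 8 makes the 24-week change in LVGLS the primary endpoint and says: "The hypothesis is that the ertugliflozin group will demonstrate superiority over the placebo group". Two bullets then give the formal hypotheses. The alternative is P₁ − P₂ < δ, and the null is its counterpart with ≥ δ. P is not defined. δ has no value in the surviving text, and it appears neither among the eight inputs that follow nor among the eight values under Real calculation. The sizing equation that Section 8 announces is missing from the text available here, so nothing is drawn from its absence. The equals sign in the null may be a misread minus sign, so nothing is drawn from that either.

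The inputs give the type I error as "5% (two-sided, default") and work in means, the first being "Mean in the ertugliflozin group". Real calculation sets the means at 17 (ertugliflozin) and 15 (placebo), both SDs at 3.5 and dropout at 18%. The narrative reads "we assumed a 15% baseline GLS in both groups and a 13.2% decrease in GLS in the ertugliflozin group after treatment", with no change on placebo.

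Elsewhere strain carries its sign. Section 5.1 says "Peak strain will be defined as the peak negative value on the strain curve during the cardiac cycle" and cites evidence that "Impaired GLS ( $>-16\%$ ) was associated with a 5.6-fold increased risk of CV mortality". Section 4.1 uses the same −16% cut-off for functional impairment. Section 2 gives the direction of the claim: "ertugliflozin will improve cardiac function in individuals with T2D and pre-heart failure".

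**The concern.** Three features of these lines look wrong together.

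- **Open margin.** With δ free, and with group 1 and signed strain as above, the alternative could mean plain superiority (δ = 0), superiority by at least some amount (δ < 0), or a non-inferiority form (δ > 0). In the last case, rejecting the null would not show benefit.
- **One direction against a two-sided alpha.** The alternative points one way, while the alpha is declared two-sided.
- **Lost sign.** On the printed scale, a fall of 13.2% from 15 does not lead to 17. The printed means also differ by +2, which lies outside P₁ − P₂ < δ when δ = 0. A test run literally in that direction on unsigned values would almost never reject.

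If these readings were really open, the trial's main conclusion would depend on a choice made after the data were in. A non-zero margin would also need a different sample size from the one planned.

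**Working it through.** **Inputs.** Section 8 and Real calculation give two-sided α = 0.05 (z = 1.960), power 80% (z = 0.8416), SD 3.5 in both groups, means 17 and 15 (absolute difference 2.0), 1:1 allocation and dropout 18%. Normal approximation throughout.

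**1. Plan's own figures.** With no margin:

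n per group = 2 × (1.960 + 0.8416)² × 3.5² / 2.0² = 48.07, so 49.

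With dropout, 49 / 0.82 = 59.8, so 60 per group and 120 in total. These match the 60 per group in Section 8 and the 120 in Section 3. The 46 per group printed at the end of Section 8 does not reproduce; its power is 78.2%. That is a separate matter.

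**2. Does the sizing leave room for a margin?** For a true signed difference of −2.0 and the alternative D < δ, the denominator becomes (2.0 + δ)². The plan states no margin, so the non-zero values below are assumptions.

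| δ | n per group | after 18% dropout |
|---|---|---|
| 0 | 48.07, so 49 | 49/0.82 = 59.8, so 60 |
| −0.5 | 85.47, so 86 | 86/0.82 = 104.9, so 105 |
| +0.5 | 30.77, so 31 | 31/0.82 = 37.8, so 38 |

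Of these, only δ = 0 gives a number that the plan prints. The unexplained 46 leads to the same place: the distance it would detect with 80% power is 3.5 × 2.8016 × √(2/46) = 2.04, which is the planned 2.0 with practically nothing left for a margin.

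**3. Sidedness.** A two-sided 5% test that claims superiority only in the favourable direction has 2.5% in that tail. The critical value is 1.960 and n is 49 whether it is written as two-sided 5% or one-sided 2.5%. A one-sided 5% test would give 37.87, so 38 per group. Dividing by 0.82 gives 46.3, close to the printed 46, but the plan labels 46 as the number before dropout and declares the alpha two-sided. I do not treat this as evidence of a one-sided design.

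**4. Scale.**

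- Signed: −15 × 1.132 = −16.98, a magnitude of about 17, as printed.
- Unsigned: 15 × (1 − 0.132) = 13.02, which is not 17.
- Relative size of the printed difference: 2/15 = 13.3%, close to the stated 13.2%.

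So 17 and 15 are magnitudes of signed values. On the signed scale the assumed difference is −17 − (−15) = −2, inside the alternative when δ = 0.

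**5. What the sign can change.** Multiplying every strain value by −1 reverses the sign of the estimated difference. Its absolute size, its standard error and the two-sided p-value stay the same. The only harmful combination is unsigned data tested in the written direction. With 49 per group, SE = 3.5 × √(2/49) = 0.7071 and power is Φ(−2.0/0.7071 − 1.960) = Φ(−4.79), below 0.01%. That would mean declaring failure because measured strain had improved, against Section 2 and the −16% definition of impairment.

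**The case for a change.** The best case for a change is that these two bullets are the only formal hypotheses in the documents. No separate analysis section defines the primary test, and Section 6.1 does not say which direction of change is benefit. A primary decision rule should not have to be inferred, and the cost of stating it is a few lines.

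Part of this stands. P and δ are loose notation, and Section 8 departs from the signed convention used elsewhere. On the printed numbers, the assumed benefit points the opposite way to the alternative.

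The rest carries less weight. Section 8 itself supplies the endpoint, the word superiority, the two-sided alpha and the two means to be compared. Sections 2, 4.1 and 5.1 together settle that more negative strain is better. A directional claim drawn from a two-sided test is ordinary practice and not a contradiction. The readings with a non-zero margin rest on values that nobody proposed and that the sizing speaks against. If the worry is that no primary analysis model is specified, that is a different and larger point, and rewording two bullets in a sample-size section would not resolve it.

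**Conclusion.** The observations about notation are correct, but no change to the plan follows. This is a clerical weakness that any analyst would fill in the same way: a two-sided 5% superiority comparison of the mean 24-week change in LVGLS, with benefit claimed only if strain is more negative on ertugliflozin. Restating the hypotheses would leave the assumed absolute difference (2.0 points), the number per group (49 evaluable, 60 with 18% dropout), the p-value and the conclusion as they are.

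This rests on two assumptions: that δ is zero, which the 60 per group and the total of 120 support, and that 17 and 15 are magnitudes of negative strain, which the 13.2% figure supports. If the missing equation set a non-zero margin, the conclusion would need another look, but neither list of inputs gives one. The conflicts among the printed sample sizes and between the two dropout rates stand apart from this point.
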